6.1. Efficacy Assessments

6.1.1. Sample Collection

Baseline breath collection will be completed within 30 minutes prior to nebulization using up to six breath collection bags. Sufficient exhaled breaths to fill the bag will be collected at each defined time point. Breath collection will be by direct exhalation into a bag, or by a breath capture device attached to the nebulizer.

Up to six post-nebulization breath samples will be collected within 10 minutes after completing the nebulized dose, at intervals of 1 minute or greater. Breath collection will be by direct exhalation into a bag, or by a breath capture device attached to the nebulizer.

Samples will be collected within ± 1 minute of the scheduled post-dose time. Actual times will be recorded for all samples as the time of first collected exhaled breath.

Sputum samples will be collected by trained study personnel per standard clinical practice within 15 minutes of the breath test. In brief, subjects will be asked to take several deep breaths and then produce a forceful cough. The subject will be encouraged to expectorate into a sample cup, and the sputum sample will be sent for culture. If the subject has difficulty producing a sputum sample, nebulized saline may be used to loosen secretions and encourage sputum production.

A oropharyngeal swab will be collected per standard clinical practice, and the sample will be preserved for microbiome analysis. A portion of the collected sputum sample will be preserved for microbiome analysis.

Sample collection will be performed according to GCP in a room in the emergency department or Clinical and Translational Sciences Center (adjacent to UNM-ED, Cohort A only).

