6.3. Safety Assessments Description

6.3.1. Clinical Laboratory Tests

During screening, subjects will have samples collected for testing as follows:

Sputum:

- Bacterial culture (only required for Cohort B)

Urine

- Pregnancy test (female subjects)

Laboratory tests do not need to be repeated if samples have already been collected as part of the presenting or admission workup for the current ED visit or hospitalization.

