6.6. Clinical Stopping Rules & Safety Data Review

This study will be discontinued if it is determined that there is a significant safety risk posed towards study subjects. Potential safety risks will be evaluated on an ongoing basis during the study by the independent medical monitor. Clinical data will be presented to the independent medical monitor in cohorts of subjects as listed in the procedure ([Section 8](#)). The independent medical monitor will adjudicate AEs and determine whether enrollment may be continued for the study. Following enrollment of the 15 subjects in Cohort A, enrollment into Cohort B will not begin until the independent medical monitor performs an overall review of safety in the cohort. If the independent medical monitor determines that no safety concerns are present, and that no increased risk is apparent for subjects with advance symptomatology (Cohort B), then enrollment may proceed with the next study Cohort. The independent medical monitor will continue to review safety data in cohorts of subjects, however enrollment may continue during review. In the event an SAE is reported in a subject, enrollment should be halted until the event can be reviewed by the independent medical monitor, and determined whether enrollment should be continued.

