7.1. Definition of an Adverse Event

An AE is defined as any untoward medical occurrence associated with the use of a drug in humans, whether or not considered drug related.

An AE may be any unfavorable and unintended sign (including an abnormal laboratory finding), symptom, or disease temporally associated with the use of a study medication, whether or not considered causally associated with the use of the study medication. Any abnormal laboratory value deemed clinically significant by the investigator, regardless of causal relationship, must be reported as an AE.

Examples of an AE include the following:

- significant or unexpected worsening or exacerbation of the condition or indication under study
- exacerbation of a chronic or intermittent preexisting condition, including either an increase in frequency or intensity of the condition (e.g., abnormal physical examination finding)
- signs, symptoms, or clinical sequelae of a suspected interaction
- signs, symptoms, or clinical sequelae of a suspected overdose of the study medication or a concurrent medication (overdose per se should not be reported as an AE or SAE, unless nonserious or serious sequelae occur)

The following examples are not considered AEs:

- medical or surgical procedure (e.g., endoscopy, appendectomy), although the condition that leads to the procedure is an AE
- anticipated day-to-day fluctuations of preexisting disease(s) or condition(s) (including laboratory values) present or detected at the start of the study that do not worsen
- the disease or disorder being studied, or expected progression, signs, or symptoms of the disease or disorder being studied, unless they become more severe or occur with a greater frequency than expected for the subject's condition

All AEs, whether volunteered, elicited, or noted on physical examination, and regardless of causality or seriousness, will be assessed and recorded on the CRF beginning after administration of study medication through approximately 2 hours after administration. SAEs (see [Sections 7.2](#) and [7.3](#)) will be assessed and recorded after administration of study medication through the last study follow-up (as described in [Section 6.4.3](#)).

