APPENDIX A. SCHEDULES OF STUDY VISITS AND PROCEDURES

Table 1: Schedule of Study Procedures

Procedure	Screening	Treatment			Follow-Up 48 Hours Post Breath Test
		Pre-Treatment	Nebulization	0-10 Minutes Post-Nebulization	
Informed Consent	X				
Inclusion/Exclusion Evaluation	X				
Demographics and Medical History	X				
Physical Examination	X				
Sputum Collection	X ^b				
Oropharyngeal Swab	X ^b				
Urine Pregnancy Test	X				
Breath Sample Collection		X ^a		X ^a	
Vital Signs	X	X	X	X	
¹³ C-urea Administration			X		
Safety Contact					X
Prior and Concomitant Medication	<----- X ----->				
Adverse Event Monitoring			<----- X ----->		

a Up to 6 samples collected pre- and post-nebulization

b Only required for Cohort B

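### AE and SAE recording starts only after the urea dose, so a non-serious reaction to induced sputum collection in Cohort B has no adverse-event entry

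*Combined protocol and SAP*

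**What the plan says.** **Recording window.** Section 7.1 states that AEs "will be assessed and recorded on the CRF beginning after administration of study medication", ending about 2 hours after the dose, and that SAEs "will be assessed and recorded after administration of study medication through the last study follow-up". Both windows open at the dose. In Appendix A, Table 1, the AE monitoring bar starts in the Nebulization column, while sputum collection sits under Screening.

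**Sputum.** Section 3.1 has Cohort B subjects give sputum before the breath test and allows it to be induced. Inclusion criterion 7 makes the ability to provide spontaneous or induced sputum a condition of entry. Section 6.1.1 adds "Sputum samples will be collected by trained study personnel per standard clinical practice within 15 minutes of the breath test" and, for subjects who have difficulty, "nebulized saline may be used to loosen secretions and encourage sputum production". The Appendix A footnote on sputum reads "b Only required for Cohort B".

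**Safety set and tables.** Section 9.3.1 limits the ITT/Safety set to subjects who receive nebulized urea. The three AE summaries in section 9.6.2 are built on severity, system organ class and preferred term. None is split by relationship or by sputum method.

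**Review.** Section 6.6 states: "Following enrollment of the 15 subjects in Cohort A, enrollment into Cohort B will not begin until the independent medical monitor performs an overall review". Later groups are reviewed while enrollment continues, except that a reported SAE halts it.

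**The concern.** A Cohort B subject can inhale nebulized saline for a study-required sample and then inhale nebulized urea a short time later. The plan opens its AE window only for the second inhalation. If the first causes a non-serious reaction such as wheeze, the plan followed to the letter gives that event no AE line, no intensity grade and no causality assessment. If the reaction stops the subject from being dosed, the subject also drops out of the safety set.

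Safety and tolerability of the breath test in pneumonia is a stated objective (section 2). A later study would presumably need sputum as its comparator again, so the tolerability of the whole sequence is useful to its designers. This study would not report it cleanly. The Cohort A review cannot be relied on to fill the gap, because sputum is not required there.

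**Working it through.** The plan states no figure on this point, so there is none to reproduce. The check sets the passages side by side and adds two short calculations.

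**1. Where a pre-dose reaction would be recorded**

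| Event | Section 7.1 / Appendix A | Elsewhere in the plan |
|---|---|---|
| Non-serious reaction to induction, subject later dosed | Before the window: no AE entry | 6.3.2: change in oxygen requirement during sample collection. 5.10 and 5.11: medications and procedures in the 7 days before urea. 3.1 and 8.1: safety committee sees the Cohort B course and each subject's safety experience |
| Same, subject never dosed | No window ever opens | Outside the safety set (9.3.1); 5.10 and 5.11 are themselves anchored to receiving urea |
| Pre-dose SAE | Before the window | 7.7: any SAE or death during the study goes to the medical monitor within 24 hours, whatever its cause |
| Reaction first seen or still present after the dose | Inside the window | 7.5.2: may be rated Not Related as the effect of another drug; 9.3.3: only a missing relationship is tabulated as related |

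The first two rows are the gap. The entries in the right-hand column are fragments and do not amount to an AE record with intensity and causality. Section 5.11 sends a treating intervention to the AE page only when there is an AE to treat, and before the dose section 7.1 recognises none.

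The third row is a contradiction between 7.1 and 7.7. It matters because section 6.6 halts enrollment when an SAE is reported. Monitoring plan 4.9.1 (Appendix E) adds to it: it calls the breath test the only study-related procedure, which overlooks induction, and it ends AE collection at 48 hours where 7.1 ends it at about 2 hours.

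In the fourth row, the event counts in all three AE summaries whatever its causality rating, because none is split by relationship.

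**2. How many subjects (assumed rates)**

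The review groups in section 8.4 have sizes 3+3+4+5+5+5+5+5+10+10+10+10 = 75. The first four make 15 (Cohort A), leaving up to 60 for Cohort B. The documents give neither the share induced nor the reaction rate. Assume 25-50% are induced:

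- Induced: 60 × 0.25 = 15 to 60 × 0.50 = 30.
- Reactions at 2%: 15 × 0.02 = 0.3 to 30 × 0.02 = 0.6.
- Reactions at 5%: 0.75 to 1.5.
- Reactions at 10%: 1.5 to 3.0.

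**3. What the Cohort A review can show about saline followed by urea**

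Let k be the number of Cohort A subjects who had both and p the true rate of a recorded event. The chance of seeing at least one event is 1 − (1 − p)^k. The one-sided 95% upper bound after no events is 1 − 0.05^(1/k).

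| k (assumed) | p = 5% | p = 10% | p = 20% | Upper bound after 0 events |
|---|---|---|---|---|
| 0 | 0 | 0 | 0 | none |
| 5 | 23% | 41% | 67% | 45% |
| 15 | 54% | 79% | 96% | 18% |

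Nothing in the plan guarantees that k is above 0.

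**The case against.** The strongest reply is that a dose-anchored window is a legitimate choice. The objective concerns the breath test, section 8.2 defines the review as covering effects after exposure to nebulized urea, and section 7.1 defines an AE by its association with study medication. Sputum is taken by ordinary clinical practice and may come from the ED workup. Saline is optional, and the 15-minute limit in 6.1.1 applies to sputum collection, with no interval given for the saline. All of this is true and limits how many subjects are affected. It does not explain why a procedure done to obtain a study-required sample should have no AE record, or why 7.1 and 7.7 disagree about a pre-dose SAE.

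Three stronger readings are tempting and are not supported:

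- **A reader might infer that induction harm never reaches the monitor.** Section 7.7 covers SAEs, 6.3.2 covers oxygen changes during sample collection, 3.1 and 8.1 put the Cohort B course before the safety committee, and the Appendix C.1 form has a space for other observations.
- **A reader might infer that such reactions are automatically charged to urea.** The remark in section 3.1 that nebulizer events appear quickly explains the observation period; it is not an attribution rule. Section 7.5.2 leaves causality to the investigator, and only a missing rating defaults to related.
- **A reader might infer that Cohort A excludes the sequence.** Sputum is not required there, but it is not barred, and Cohort B has its own reviews (Groups 5 to 12).

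**Conclusion.** The gap is real and modest. Following the plan exactly leaves non-serious, pre-dose induction reactions without an AE entry, leaves reacting but never-dosed subjects outside the safety set, and gives two answers on pre-dose SAEs. This rests on the text alone and not on any assumed rate.

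The size is uncertain. Over the assumed ranges above, 0.3 to 3 reactions would lack an AE line. The documents give no urea event rate that would allow a numerical comparison.

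That the Cohort A review may contain no subject with saline followed by urea is a limitation to state. Better recording does not make that review test the sequence. Nor does a timing tag separate a delayed saline reaction from a urea reaction; it makes the overlap visible. The point should be corrected, but it does not invalidate the safety analysis of urea.

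**What to change.** 1. Reconcile section 7.1, section 7.7, the Appendix A bar and monitoring plan 4.9.1 so that AE and SAE recording starts at the first study-specific procedure after consent, sputum induction included. Extend the AE definition in 7.1 to match, and settle the end of the window at the same time.
2. Tag each event on the CRF as before or after the start of urea.
3. In section 9.6.2, report pre-dose procedure events separately from post-urea events. Include subjects who were never dosed, who need a line outside the Safety set. Enter pre-dose events on the Appendix C.1 form.
4. List Cohort B AEs by induced or spontaneous sputum. Appendix E section 4.8 already requires the collection method and times as source data, so subjects with saline followed by urea can be identified from Group 5, the first Cohort B review.
5. State as a limitation that the Cohort A review may include no such subject.

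Cost: amendment wording, a timing tag, a small change to the review form and one extra listing. No procedure or visit is added. The downside is a few more procedure-related AEs to record and review.

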7.2. Definition of a Serious Adverse Event

An SAE is defined as any event that meets the following criteria:

- It results in death or is life-threatening (i.e., presents an immediate risk of death from the event as it occurred). (This criterion is not intended to include an AE that, had it occurred in a more severe form, might have caused death.)
- It results in persistent or substantial disability or incapacitation. (This criterion is not intended to include experiences of relatively minor medical significance, such as uncomplicated headache, diarrhea, or sprained ankle.)
- It results in unplanned hospitalization.
- It results in prolongation of an existing hospitalization.
- It is a congenital anomaly or birth defect.
- It requires medical or surgical intervention to prevent any of the above outcomes.

Medical and scientific judgment should be exercised in determining whether an AE is serious when considering important medical events that may not be immediately life-threatening or result in death or hospitalization, but may jeopardize the subject or may require intervention to prevent any of the other outcomes listed. Examples of such medical events that may also be considered serious include, but are not limited to, intensive treatment in an emergency room or at home for allergic bronchospasm, blood dyscrasias, or convulsions that do not result in hospitalization.

Hospitalization for elective treatment of a preexisting condition that did not worsen from baseline does not meet the definition of an SAE.

Social or convenience admission to a hospital or prolongation of a hospitalization for social or convenience reasons not associated with the occurrence of an AE does not meet the definition of an SAE.

7.2.1. Serious Adverse Events That Occur After Study Completion

If an investigator becomes aware of an SAE or death that occurs in a subject more than 48 hours after the subject receives study medication and that investigator considers the event to be related to the study medication, the investigator is obligated to report the SAE.

7.3. Definition of a Suspected Adverse Reaction (SAR)

A SAR is defined as any adverse event for which there is a reasonable possibility that the adverse event was caused by the study drug. For the purposes of safety reporting, ‘reasonable possibility’ means there is evidence to suggest a causal relationship between the drug and the adverse event. A suspected adverse reaction implies a lesser degree of certainty about causality than adverse reaction, which means any adverse event caused by a drug.

7.4. Definition of a Serious Suspected Adverse Reaction (SSAR)

A SSAR is any Suspected Adverse Reaction (SAR) that is determined to be serious, based on the outcomes of a SAE described in Section 7.2; i.e. death, life-threatening, causes or prolongs

inpatient hospitalization, causes a persistent or significant incapacity or substantial disruption of the ability to conduct normal life functions, or a congenital abnormality/birth defect.

7.5. Recording and Evaluating Adverse Events and Serious Adverse Events

The investigator will attempt to establish a diagnosis of the event on the basis of signs, symptoms, or other clinical information. In such cases, the diagnosis, not the individual signs or symptoms, should be documented as the AE or SAE.

7.5.1. Assessment of Intensity

The investigator will make an assessment of intensity for each AE and SAE reported during the study, using his or her clinical judgment. The intensity of each AE and SAE recorded on the CRF should be assigned to one of the following categories:

- **mild:** an event that is easily tolerated by the subject, causes minimal discomfort, and does not interfere with everyday activities
- **moderate:** an event that is sufficiently discomforting to interfere with normal everyday activities
- **severe:** an event that prevents normal everyday activities

An AE that is assessed as severe should not be confused with an SAE. *Severity* is a term used to describe the intensity of a specific event, and both AEs and SAEs can be assessed as severe. The event itself, however, may be of relatively minor medical significance (such as a severe headache). This is not the same as *serious*, which is based on the subject's or event's outcome or on action criteria usually associated with events that pose a threat to a subject's life or functioning (see [Section 7.2](#)).

7.5.2. Assessment of Causality

The investigator is obligated to use his or her clinical judgment to assess the relationship between the study medication and the occurrence of each AE or SAE. The investigator will assess the relationship to the study medication by using the following criteria:

- **Definitely Related:** An AE has a strong temporal relationship to the study drug. The AE is most likely explained by study drug. Dechallenge and rechallenge (if possible) are positive. The AE is consistent with a known response to the study drug. Another etiology is unlikely or significantly less likely.
- **Probably Related:** An AE has a strong temporal relationship to the study drug. The AE is more likely explained by study drug than by another cause. Dechallenge (if performed) is positive.
- **Possibly Related:** An AE has a reasonable temporal relationship to study drug. The AE could have been due to another equally likely cause. Dechallenge is positive.
- **Not Related:** The subject did not receive the study drug **OR** the AE has no temporal relationship to study drug **OR** the AE has a much more likely alternate etiology **OR** the AE is due to an underlying or concurrent illness or effect of another drug.

Even in situations in which minimal information is available for the initial SAE report, it is important that the investigator always make an assessment of causality for every event before transmitting the SAE reporting form and AE CRF page(s) to the medical monitor. The causality assessment is one of the criteria used when determining regulatory reporting requirements. The investigator may change his or her opinion of causality in light of follow-up information and amend the SAE reporting form and AE CRF page(s) accordingly.

7.5.3. Assessment of Outcome

All SAEs must be followed until they are resolved, the condition stabilizes, the events are otherwise explained, or the subject is lost to follow-up. The investigator will assess the outcome of the event by using the following terms:

- **Resolved:** The event resolved or the subject recovered without sequelae. An event (either serious or nonserious) occurred and had an endpoint, and the subject experienced no restrictions. Examples include stent placement for coronary artery disease (a device implanted is not a sequela), an appendectomy (a scar is not a sequela), a postoperative wound infection, or an upper respiratory tract infection.
- **Resolved with sequelae:** The event has at least one secondary outcome that may result in permanent disability, functional limitation, or both. Such sequelae are usually limited to SAEs. Examples include hip replacement resulting in foot drop (foot drop is not the intended outcome but is a risk of surgery), stroke resulting in paralysis, or emboli formation after a bacterial infection resulting in a renal infarct and loss of renal function.
- **Not resolved:** At the end of the study, a nonserious event either has not changed in intensity or may not have recovered to baseline values, and the outcome is unknown. Examples include headache, low-grade fever, or nausea.
- **Unknown:** The subject has withdrawn from the study prematurely or is lost to follow-up, and the status of the event is unknown.
- **Death**

7.5.4. Assessment of Expectedness

For the purposes of safety reporting, adverse events and suspected adverse events should be assessed as being expected or unexpected. An AE or SAR is considered unexpected if it is not listed in the investigator brochure or is not listed at the specificity or severity that has been observed; or, if an investigator brochure is not required or available, is not consistent with the risk information described in the general investigational plan or elsewhere in the current application.

7.6. Follow-up of Adverse Events and Serious Adverse Events

Nonserious AEs will be followed after the study visit, until an appropriate resolution can be documented.

After the occurrence of an AE or SAE, the investigator is required to follow each subject proactively and provide further information on the subject's condition. All AEs and SAEs

documented at a previous visit or contact are designated as ongoing and will be reviewed at subsequent visits or contacts.

SAEs will be followed until the event resolves, the condition stabilizes, the event is otherwise explained, or the subject is lost to follow-up. The investigator will ensure that follow-up information includes results of any additional laboratory tests or investigations, histopathologic examinations, or consultations with other healthcare professionals that serve to clarify the nature of the event, the cause of the event, or both.

New or updated information will be recorded on the originally completed SAE reporting form and CRF pages, with all changes signed and dated by the investigator. The updated SAE reporting form and CRF pages should be resubmitted within the time frames outlined in [Section 7.7](#).

